### 5.4 Prior and Concomitant Medications

Prior therapies and medications are those which began and were stopped before receipt of study medication. Concomitant therapies and medications are those which were ongoing at the receipt of study medication and those which were taken during the study (i.e., between the date of first dose and the last study visit).

A horizontal bar chart with six bars of increasing length from left to right. The first bar is the shortest, followed by a small gap, then a medium bar, a long bar, and two very long bars. The bars are black on a white background.

## 5.7 FACE-Q

The FACE-Q assessments will be scored and converted to a transformed score which ranges from 0 to 100 according to scoring rules for the assessment. Section 8.1 for scoring of the FACE-Q Satisfaction with Forehead and Eyebrows; and, Section 8.2 for scoring of the FACE-Q Appraisal of Lines: Forehead.

## 5.8 Adverse Events

Treatment-emergent AEs are those AEs with an onset on or after the date and time of trial treatment or events which were present before treatment and which worsened after treatment.

AEs with missing severity will be summarized as “severe”. AEs with missing relationship will be summarized as “related”.

## 6. STATISTICAL METHODS

All statistical programming will be performed using statistical analysis system (SAS) version 9.4 or higher.

1. **What is the primary purpose of the proposed legislation?**

## 6.1 Subject Disposition

The number and percentage of subjects who have signed informed consent, enrolled, received each treatment (GL and FHL), and completed visits will be tabulated by summary cohort and overall; and, included in a listing. Reasons for not completing the study will also be tabulated by summary cohort and overall using numbers and percentages; this data will also be included in a listing. For those subjects who are considered to have failed screening, the reason(s) for failure will be provided in a listing.

The number and percentage of subjects included and excluded from the analysis populations will be tabulated overall and for each summary cohort. Reason(s) for exclusion from each population will be summarized and listed.

## Statistical Analysis Plan for 1820202

A summary of the duration of the subject participation in the study will be produced, including the n, mean, standard deviation (SD), median, first and third quartiles, minimum, and maximum duration in weeks, as well as the number and percentage of subjects in the duration categories.

Major protocol deviations will be listed and summarized by summary group.

## 6.2 Demographic and Baseline Characteristics

Descriptive statistics will be used to summarize demographic and baseline characteristics by summary cohort and overall.

Demographic data include age, age category, sex, ethnicity, and race. Baseline characteristics include prior Botulinum toxin Type in the GL and FHL, time since last prior Botulinum toxin Type A injection in the GL and FHL, and Fitzpatrick skin type, as well as the baseline values of the efficacy assessments, PFWS, PHFWS, IGA-FWS, and IGA-FHWS. Summaries will be produced for the Enrolled population. If the GL Evaluable, FHL Evaluable, or Safety FHL population differs from the Enrolled population, then the summaries will be produced for the population(s) which differ from the Enrolled population.

## 6.3 Medical History

Medical history will be classified on the basis of MedDRA terminology, using the latest terminology at the time of database finalization. Medical history will be summarized for the Safety FHL population by summary cohort and overall, by system organ class, and by preferred term; and, will be listed.

## 6.4 Prior and Concomitant Medications

Prior therapies/medications and concomitant therapies/medications will be coded using the World Health Organization (WHO) drug dictionary and summarized by Anatomical Therapeutic Chemical (ATC) second level term and Preferred Name for the Safety population. Prior and concomitant medications will be summarized separately.

## 6.5 Efficacy Analyses

Descriptive statistics will be provided for all efficacy variables at all visits by cohort. A 95% exact CI will be provided for proportions. All analyses displaying proportions will use population counts as denominators at all visits regardless of the number of actual observations recorded. Differences between cohorts will not be presented except where specifically identified in the shells.

The Efficacy GL population will be used when analyzing endpoints associated with GL.

[figure not shown]
The Efficacy FHL population will be used when analyzing endpoints associated with FHL.

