### 9.3. Statistical Analyses

The statistical analysis plan will be developed and finalized before database lock and will describe the detailed methods of analysis, the subject populations to be included in the analyses, and procedures for accounting for missing, unused, and spurious data. This section is a summary of the planned statistical analyses of the primary and secondary endpoints.

In general, descriptive summaries will include means, standard deviations, and ranges for continuous variables; and counts and proportions for categorical measures. Unless otherwise stated, a 95% CI will be provided for means and proportions. No formal hypothesis tests are planned, but may be performed as exploratory analyses. No multiplicity adjustments or imputation of missing data are planned.

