### 3. OVERALL STUDY DESIGN AND PLAN

#### 3.1 Study Design

[figure not shown]
This is a phase 2a, multicenter, open-label, dose-escalation study to evaluate the safety and efficacy of DAXI for injection for the treatment of subjects with moderate to severe FHL in conjunction with GL treatment. This study will be conducted at 4 sites in the United States and Canada.

Subjects will be screened for eligibility and enrolled into the study after providing informed consent.

[figure not shown]
Approximately 60 subjects (18-65 years of age) with moderate to severe FHL will be enrolled

[figure not shown]
The total study duration will be up to 40 weeks including up to 2 weeks for screening. Subjects will be followed for a minimum of 24 weeks from GL treatment for safety or until all scores on the IGA-FWS and PFWS, as well as the IGA-FHWS and PFHWS return to baseline (Day 1 Visit prior to GL treatment) or until Week 38, whichever occurs first. Subjects will then have a Final Evaluation Visit. The intention is for subjects to be followed for a minimum of 24 weeks from FHL treatment (Week 26).

A Data Review Committee (DRC) will be used to review data from each cohort and will determine whether to proceed to the next cohort. If the DRC elects not to proceed with the FHL injection in a given dose cohort, subjects assigned to that cohort who have already received GL treatment will be followed for 14 weeks from the time of treatment (Day 1).

[figure not shown]

Statistical Analysis Plan for 1820202

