### **4.3 FHL-Evaluable Population**

All enrolled subjects who receive the FHL treatment and have any post-FHL treatment assessment of IGA-FHWS at maximum eyebrow elevation.

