### 6.5.1 Primary Efficacy Analysis

The proportion of subjects achieving a score of 0 or 1 (none or mild) on the IGA-FHWS at maximum eyebrow elevation at Week 6 will be summarized. Subjects with no data at Week 6 after imputation of worst value will be considered to not meet the criteria (i.e., are imputed as non-responders). An exact 95% confidence intervals for the individual proportions will also be provided. A Cochran-Mantel-Haenszel test of association, stratified by stratified by baseline IGA-FHWS severity and study center, will be performed. In addition, an exact Cochran-Armitage test for trend, ignoring the stratification factors, will be performed. If the Cochran-Mantel-Haenszel test is significant at the 0.05 significance

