## 6.7 Changes from the Planned Analyses

The primary analysis to explore dose response was planned to be an exact logistic regression stratified by study center and baseline severity, however, the conditional distribution is degenerate. A logistic regression may still be performed, but the primary analysis has been changed to a Cochran-Mantel-Haenszel statistic supplemented with the Cochran-Armitage test for trend. If the Cochran-Mantel-Haenszel test is significant, then a linear regression with dose as the predictor will be performed.

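### Fixed denominators give an unassessed GL-only cohort a 0% GL response after Week 14, and the Week 6 missing-data rule is uneven and not reconciled with the protocol

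*SAP*

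**What the plan says.** **Denominators.** SAP 6.5 states: "All analyses displaying proportions will use population counts as denominators at all visits regardless of the number of actual observations recorded". GL endpoints use a GL population. For the forehead, "The Efficacy FHL population will be used when analyzing endpoints associated with FHL". That name is not among the five populations in SAP section 4, and I take it to mean FHL-Evaluable.

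**Populations.** SAP 4.3 defines FHL-Evaluable as "All enrolled subjects who receive the FHL treatment and have any post-FHL treatment assessment of IGA-FHWS at maximum eyebrow elevation". SAP 4.2 defines GL-Evaluable in parallel, needing only some frown rating after the GL injection. Protocol 9.2 gives the same definitions. Safety-FHL (SAP 4.5) is everyone who received FHL treatment, assessed or not.

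**Planned follow-up.** Subjects are followed until all four severity scales are back at baseline, subject to a 24-week minimum, or until Week 38. There is one exception. If the DRC does not go ahead with FHL treatment in a cohort, "subjects assigned to that cohort who have already received GL treatment will be followed for 14 weeks from the time of treatment (Day 1").

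**Missing data.** Protocol 9.3 says "No multiplicity adjustments or imputation of missing data are planned". The same section also assigns to the SAP the "procedures for accounting for missing, unused, and spurious data". For the primary endpoint SAP 6.5.1 then says: "Subjects with no data at Week 6 after imputation of worst value will be considered to not meet the criteria (i.e., are imputed as non-responders").

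**Declared changes.** SAP 6.7 lists one departure, in the dose-response test: "the primary analysis has been changed to a Cochran-Mantel-Haenszel statistic supplemented with the Cochran-Armitage test for trend". It does not mention missing data.

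**The concern.** A fixed denominator makes an absent subject count against the response rate. That is reasonable when absence suggests failure. It is not reasonable when the plan itself ends follow-up without regard to response, as it does for GL-only subjects of a halted cohort. Their GL response from Week 18 onward would be printed as a rate with a confidence interval although no data lie behind it, and a reader could take it for rapid loss of effect.

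On the primary endpoint the matter is consistency. Two treated subjects who both lack a Week 6 score can be handled in opposite ways: one is a failure and the other leaves the analysis. The subject with less data does less harm to the rate. The imputation itself appears only in the SAP, against a protocol statement that none is planned, and the section meant to record such changes is silent. With about 15 subjects per cohort, one subject moves the rate by several points.

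**Working it through.** There is no power-based figure to reproduce, since SAP 3.1.1 says the sample size was not set by power. The planned size agrees with itself: 4 cohorts × 15 = 60. The documents give no dropout rate or expected response, so the responder and missing counts below are assumptions for illustration.

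**1. GL-only subjects of a halted cohort**

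Inputs: 15 per cohort (Protocol 4.1); follow-up of 14 weeks from Day 1 (SAP 3.1); later visits at Weeks 18, 22, 26, 30, 34 and 38 (Protocol 4.4); exact 95% intervals (SAP 6.5).

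- Each subject with one frown rating after GL treatment is GL-Evaluable and stays so at all visits.
- From Week 18 nobody is seen, so the numerator is 0 and the rate is 0/15 = 0%.
- The exact upper limit for zero events is 1 − 0.025^(1/15) = 1 − 0.782 = 0.218, so the interval is 0 to 21.8%.
- If 5 to 12 of the 15 were still responding (33% to 80%), the printed result would be the same at each of the six later visits.

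These subjects never receive FHL treatment, so they are not FHL-Evaluable and do not enter the primary endpoint.

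**2. Subjects who leave because all scores returned to baseline**

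Entry requires a score of 2 or 3 on all four scales at maximum contraction (Protocol 5.1), and response means 0 or 1. A subject back at baseline is therefore a true non-responder on that endpoint. Suppose 6 of 15 have left this way and 4 of the remaining 9 respond:

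- fixed denominator: 4/15 = 26.7% (exact CI 7.8 to 55.1%)
- observed cases: 4/9 = 44.4% (13.7 to 78.8%)

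If a returned score stays returned, the fixed figure is the right one. The denominator rule is sound for this group.

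**3. Treated subjects with no rating after FHL treatment**

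Take 15 FHL-treated subjects, with d of them never rated afterwards.

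| Responders | d | FHL-Evaluable | All FHL-treated |
|---|---|---|---|
| 14 | 1 | 14/14 = 100% | 14/15 = 93.3% |
| 12 | 1 | 12/14 = 85.7% | 12/15 = 80.0% |
| 12 | 2 | 12/13 = 92.3% | 12/15 = 80.0% |

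A subject rated at Week 4 but not at Week 6 stays in the denominator of 15 and is a non-responder, unless the worst-value step supplies a score.

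**4. Imputing non-response or not**

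Take 15 FHL-Evaluable subjects, 12 of them true responders, with m of those 12 missing at Week 6. The imputed rate is (12 − m)/15 and the observed-case rate is (12 − m)/(15 − m).

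| m | Non-response imputed | Observed cases |
|---|---|---|
| 0 | 80.0% | 80.0% |
| 1 | 11/15 = 73.3% | 11/14 = 78.6% |
| 2 | 10/15 = 66.7% | 10/13 = 76.9% |
| 3 | 9/15 = 60.0% | 9/12 = 75.0% |

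Each missing true responder lowers the imputed rate by 1/15 = 6.7 points. This column assumes that the worst-value step supplies no score for them.

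**The case against.** The strongest reply is that the fixed denominator is mostly right. A reader might infer that all subjects whose follow-up ends by design are wrongly counted as failures. The documents do not support that. The usual early exit is a return of every score to baseline, which is non-response at maximum contraction, so limiting denominators to subjects still in planned follow-up would inflate late rates (step 2). This reply stands, and it confines the defect to the GL-only group. It rests on reading 24 weeks as a minimum, which is how the text describes it. It does not carry over to scores at rest, where the entry criteria set no floor.

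The GL-only problem is also conditional. It arises only if the DRC withholds FHL treatment after GL dosing, and duration is summarised separately by Kaplan-Meier methods (SAP 6.5.3.2). A reader might go on to infer a ceiling of 45/60 = 75% on a GL rate pooled over all subjects. Visible SAP text presents efficacy by cohort, so that figure has no basis. The section on summary groups is blacked out, so placing these subjects in their own cohort relies on SAP section 4, which uses planned assignment for this population.

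On imputation, Protocol 9.3 leaves missing-data procedures to the SAP and defines no observed-case denominator. It would go too far to say that the two documents prescribe two different primary rates. Non-response imputation is a defensible choice. What remains is that the protocol also says outright that no imputation is planned, and the departure is undeclared. The worst-value step is not defined in the visible text and may be defined in a redacted section, so how often imputation to non-response would apply is unknown.

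On the population, protocol and SAP agree, so there is no conflict between documents, and exclusions are tabulated with reasons (SAP 6.1). That makes the exclusion visible but does not show its effect on the rate.

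**Conclusion.** The point holds in three limited parts.

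1. For GL-only subjects of a DRC-halted cohort, the stated rule produces an artefact of up to 0/15 (0 to 21.8%) at every visit after Week 14. This depends on a halt after GL dosing, on the whole cohort of 15 having been dosed, and on grouping by planned assignment.
2. The Week 6 analysis is uneven. It penalises a missing Week 6 score but removes a treated subject with no later rating. One such subject is worth roughly 6 to 7 points at 15 per cohort, under assumed counts. This is a weakness shared by both documents.
3. SAP 6.5.1 departs from the no-imputation statement in Protocol 9.3 without a record in SAP 6.7. This is a gap in documentation. It does not make the imputation wrong.

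The study is an open-label, descriptive phase 2a trial, so no formal decision rule is at risk. The descriptive response rates are its main efficacy output, however, and these rules decide what they mean.

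**What to change.** - **SAP 6.5:** remove only the GL-only subjects of a DRC-halted cohort from GL responder denominators after Week 14, and show them as not assessed. State that subjects who leave on return to baseline remain in as non-responders on the 0/1 endpoints at maximum contraction. Use the population names defined in section 4.
- **SAP 6.5.1:** report the Week 6 responder rate on all FHL-treated subjects (Safety-FHL) with non-response imputation, at least as a sensitivity analysis, and add an observed-case analysis.
- **SAP 6.7:** reconcile Protocol 9.3 with SAP 6.5.1 and list the imputation as a change from plan.

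The cost is a few sentences and one or two extra table rows. No new data or new population is needed. The Safety-FHL rate can come out slightly lower than the FHL-Evaluable rate.

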### 6.5.1 Primary Efficacy Analysis

The proportion of subjects achieving a score of 0 or 1 (none or mild) on the IGA-FHWS at maximum eyebrow elevation at Week 6 will be summarized. Subjects with no data at Week 6 after imputation of worst value will be considered to not meet the criteria (i.e., are imputed as non-responders). An exact 95% confidence intervals for the individual proportions will also be provided. A Cochran-Mantel-Haenszel test of association, stratified by stratified by baseline IGA-FHWS severity and study center, will be performed. In addition, an exact Cochran-Armitage test for trend, ignoring the stratification factors, will be performed. If the Cochran-Mantel-Haenszel test is significant at the 0.05 significance

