**Overall Design:**

This is a phase 2a, multicenter, open-label, dose-escalation study to evaluate the safety and efficacy of DAXI for injection for the treatment of subjects with moderate to severe FHL in conjunction with treatment of the glabellar complex. This study will be conducted at 4 sites in the United States and Canada.

Approximately 60 subjects (18 years to 65 years of age) with moderate to severe FHL will be enrolled sequentially into 1 of 4 treatment cohorts (15 subjects per cohort) to receive DAXI for injection [REDACTED]. Investigators will make all reasonable efforts to enroll equal proportions of patients with moderate and severe FHL (based on baseline assessments) in each dosing cohort. Baseline for all cohorts will be defined as the Day 1 Visit prior to GL treatment. At the Day 1 study visit, subjects will receive a single 40 U dose of DAXI for injection for treatment of GL. At the Week 2 Visit, subjects will receive the assigned dose of DAXI for injection for the treatment of FHL. The total study duration will be up to 40 weeks including up to 2 weeks for screening. Subjects will be followed for a minimum of 24 weeks from GL treatment for safety or until all scores on the IGA-FWS and PFWS, as well as the IGA-FHWS and PFHWS return to baseline (Day 1 Visit prior to GL treatment) or until Week 38, whichever occurs first. Subjects will then have a Final Evaluation Visit. If the Data Review Committee (DRC) elects not to proceed with the FHL injection in a given dose cohort, subjects assigned to that cohort, who have already received GL treatment, will be followed for 14 weeks from the time of treatment (Day 1).

All treatments will be IM injections administered by the principal investigator (PI). [REDACTED]

[REDACTED]

The decision to treat subsequent cohorts with the FHL dose will be based upon review of the data by the DRC (refer to Section 9.4.1 for additional information). Revance has the right to stop or terminate the study at any time, for any reason, at their discretion or in consultation with the DRC.

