### **9.3.1. Efficacy Analyses**

Unless otherwise noted, baseline for all efficacy assessments for GL refers to the last available assessment prior to GL treatment for those associated with GL severity and for FHL refers to the last available assessment prior to FHL treatment for those associated with FHL severity.

The primary efficacy endpoint will be the proportion of subjects achieving a score of 0 or 1 (none or mild) on the FHWS as assessed by IGA-FHWS at maximum eyebrow elevation at Week 6. The dose response in the proportion of responders at 4 weeks after the FHL treatment (Week 6) will be explored using the logistic regression stratified by baseline FHWS severity (last assessment prior to GL treatment at Day 1 Visit) and study center to assess the dose-response. Additional measures to assess the effectiveness outcomes will include the IGA-FHWS, PFHWS, GAIS evaluated at maximum contraction (eyebrow elevation) and at rest at each visit. Various responder endpoints associated with the FHWS, such as achieving certain status or certain magnitude of improvement from baseline, will be derived from these effectiveness outcomes for each visit. These responder endpoints will be analyzed by statistical models similar to that for the primary endpoint.

Duration of response will be evaluated by various time-to-event endpoints. Kaplan-Meier curves will be plotted by dose group for each time-to-event endpoint and median duration with associated 95% CIs will be provided.

Similar responder and time-event endpoints associated with the GL wrinkle severity defined based on the assessments for GL wrinkle severity such as IGA-FWS, PFWS or GAIS on GL, will be summarized similarly to those endpoints associated with FHWS. Efficacy outcomes will be summarized. Descriptive statistics will be provided for all efficacy variables at all timepoints. Note that exploratory analyses of the change in FHL severity from Day 1 (post-GL treatment) to Week 2 and from pre-FHL treatment (Week 2 pre-treatment) to post treatment will also be performed.

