### **3.1.2 Treatments Administered**

This is an open-label, non-randomized study. Subjects will be sequentially enrolled by cohort. All subjects will receive DAXI for injection according to assigned cohort.

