#### 6.5.4 Adjustments for Covariates

The analysis of the primary endpoint requires a stratified exact logistic regression model be run, where the strata are created based on the baseline IGA-FHWS severity and study site, both of which are considered to be covariates.

[REDACTED]

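### The one firmly planned, explicitly dose-ordered test ignores baseline severity and center in a non-randomized, sequentially filled trial; a severity-stratified trend test is better protected and more powerful

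*SAP*

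**What the plan says.** SAP 6.5.1 plans two tests on the Week 6 IGA-FHWS responder endpoint. The first is stratified: "A Cochran-Mantel-Haenszel test of association, stratified by stratified by baseline IGA-FHWS severity and study center, will be performed". The second is not: "an exact Cochran-Armitage test for trend, ignoring the stratification factors, will be performed". SAP 6.7 gives the history. The exact stratified logistic regression proved degenerate, so "the primary analysis has been changed to a Cochran-Mantel-Haenszel statistic supplemented with the Cochran-Armitage test for trend".

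The only alpha is attached to the CMH test. The sentence that begins "If the Cochran-Mantel-Haenszel test is significant at the 0.05 significance" opens a follow-up linear regression, in which dose is categorical according to 6.5.1 and simply dose according to 6.7. An unstratified logistic regression is optional.

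Protocol 9.3.1 intended an adjusted analysis: the dose response "will be explored using the logistic regression stratified by baseline FHWS severity" and by study center. SAP 6.5.4 still requires the exact stratified logistic model, in which "the strata are created based on the baseline IGA-FHWS severity and study site, both of which are considered to be covariates".

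On allocation, SAP 3.1.2 states: "This is an open-label, non-randomized study. Subjects will be sequentially enrolled by cohort". Protocol 4.1 asks investigators to try to enroll moderate and severe subjects equally in each cohort, without a cap or quota. The visible text has no such rule for center. Protocol 9.3 treats any hypothesis test as exploratory.

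**The concern.** The exact Cochran-Armitage test takes its reference distribution from shuffling all analyzed subjects freely across the four cohorts. Its null is that subjects are exchangeable across cohorts. The question in Protocol 9.3.1 is different: is there a dose effect given severity and center? Randomization would bring the two nulls together; sequential filling does not.

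Severity bears directly on the endpoint. Entry requires a score of 2 or 3 and response is 0 or 1, so a severe subject must improve by two grades and a moderate subject by one. If later cohorts hold fewer severe subjects, a trend can appear without a dose effect. The reverse drift can hide a real one. Even without drift, ignoring a strong prognostic factor costs power. This test is the natural place for a reader to look for dose response.

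**Working it through.** **Inputs from the documents.** 4 cohorts x 15 = 60, which matches the stated approximate total (Protocol 4.1). There are 4 centers. No power, effect size or error rate is given for the trend test, and SAP 3.1.1 says that power did not set the sample size, so there is no planned operating figure to reproduce.

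**Assumptions.** Two-sided 0.05 for the trend test; dose scores 1, 2, 3, 4 (only the cohort 4 dose is visible); all response rates, drift patterns and dose slopes.

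**Test statistic.** T = Σ d_j R_j, with score d_j and R_j responders in cohort j.

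- Unstratified: given R responders in total, P(r_1,…,r_4) = Π C(15, r_j) / C(60, R), and E(T) = 2.5R.
- Stratified: T is summed over strata s, and the reference probability is Π_s [Π_j C(n_sj, r_sj) / C(N_s, R_s)].
- In both, p = P(|T − E(T)| ≥ |t − E(T)|), and the test rejects if p ≤ 0.05.

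**How drift makes a trend.** The cohort rate is [m × 0.9 + (15 − m) × 0.5] / 15 for m moderate subjects. With m = 4, 6, 9, 11 this gives 9.1/15, 9.9/15, 11.1/15 and 11.9/15, that is 61%, 66%, 74% and 79%, with no dose effect at all.

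**Rejection rate of the unstratified test, no dose effect (full enumeration).**

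| Moderate per cohort | 90%/50% | 90%/60% | 95%/85% |
|---|---|---|---|
| 8, 7, 8, 7 | 2.0% | 2.4% | 2.7% |
| 6, 7, 8, 9 | 4.0% | 3.7% | 3.0% |
| 5, 7, 8, 10 | 7.6% | 5.8% | 3.4% |
| 4, 6, 9, 11 | 16.3% | 10.8% | 4.3% |
| 3, 6, 9, 12 | 26.1% | 16.4% | 5.2% |

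Columns give moderate/severe response. The severity-stratified exact trend test rejects in 2.8% to 4.2% of trials in all 15 cells. Inflation starts at about 5, 7, 8, 10, where the moderate share goes from 5/15 = 33% to 10/15 = 67%. Scores 1, 2, 3, 5 or 1, 2, 4, 5 move the figures by at most about 3 points.

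**Power with a true effect** (log-odds 0.7 per cohort; 75% moderate and 40% severe response in cohort 1). The first two columns are enumerated; the last two come from 3,000 simulated trials per scenario.

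| Moderate per cohort | Unstratified trend | Severity-stratified trend | Severity-by-center trend | CMH, general association |
|---|---|---|---|---|
| 8, 7, 8, 7 | 52.6% | 62.7% | 61.9% | 44.8% |
| 11, 9, 6, 4 | 25.0% | 55.9% | 55.4% | 37.9% |
| 12, 9, 6, 3 | 19.2% | 49.9% | 51.0% | 34.2% |

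**Center drift alone** (no dose effect, severity balanced, assumed center response rates of 50%, 65%, 85% and 95%; 3,000 trials). Under moderate and strong drift the unstratified test rejects in 15.9% and 40.0% of trials, the severity-stratified test in 17.1% and 41.9%, and the severity-by-center test in 4.0% and 4.4%. Severity strata alone therefore do not deal with center.

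**The case against.** **An adjusted test is already primary.** The CMH test is stratified by both factors and holds about 4% in these scenarios. This stands, and it limits the harm. It does not fill the gap. The SAP does not say which CMH statistic is meant, and under general association the power for an ordered effect is 34% to 45%, against 51% to 62% for the severity-by-center trend test.

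**Severity balance is sought in every cohort.** This stands too: where balance holds or drift is mild, the table shows no inflation. SAP 6.2 tabulates baseline IGA-FHWS by cohort, so a failure would be seen, and the protocol synopsis says the effect of center and severity will be explored. But the balance rule is best effort, it does not cover center, and the power gain from stratifying exists even in balanced cohorts.

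**The assumed rates may be too low.** SAP 6.7 reports degeneracy. In simulation the eight-stratum conditional distribution collapsed in 0% of trials at 90%/60% response, 1.8% at 97%/90%, 16% at 99%/95% and 53% at 99%/99%. With 4, 6, 9, 11 or 3, 6, 9, 12 moderate subjects, the unstratified test rejects in only 3.4% or 3.9% at 97%/90%, and 1.1% or 1.4% at 99%/95%. If response is that high, severity drift does no harm to the level. The SAP does not say whether the degeneracy arose with categorical or numeric dose, so it does not settle the response rate.

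**The consequence is limited.** Testing is exploratory, and no visible text uses the trend p-value to choose a dose; escalation rests on the Data Review Committee. Redacted parts around SAP 6.5.4 may hold further analyses. All of this stands.

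**Conclusion.** The point holds as a recommended improvement. The unstratified trend test is the only firmly planned, explicitly dose-ordered test in the visible SAP, and it drops the two factors by which the protocol meant to stratify. With no dose effect and 90% moderate / 50% to 60% severe response, it rejects in about 6% to 8% of trials when the moderate share runs from one third to two thirds, and in 11% to 26% under stronger drift. With the assumed true effect it has 53% power against 63% for the severity-stratified test in balanced cohorts, and 19% to 25% against 50% to 56% when drift opposes the effect. All of these rest on assumed rates, slopes and drift.

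A reader might infer more than the documents support:

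- *That this is the only dose-ordered analysis.* A CMH correlation statistic would be ordered and stratified, 6.7 can be read as regression on numeric dose, 6.5.4 still requires an exact logistic model, and an optional logistic regression is allowed.
- *That a primary or confirmatory conclusion is invalid.* The test is an exploratory supplement to a stratified CMH test.
- *That its null covers all 60 subjects.* The analysis set is the FHL-Evaluable population (called Efficacy FHL in 6.5), and 60 is approximate.
- *That inflation is to be expected.* It needs roughly 67/33 drift in severity, or drift in center, and largely disappears at high response rates.

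**What to change.** 1. In SAP 6.5.1, make the exact trend test permute only within the two baseline IGA-FHWS severity strata, in the FHL-Evaluable population. State the dose scores, sidedness and alpha. Keep the unstratified test as a descriptive supplement.
2. Report a severity-by-center stratified version beside it, because severity strata alone leave center drift uncorrected. For numeric dose this version shares its conditional distribution with the exact stratified logistic model, so the degeneracy in 6.7 may recur. If it does, say so and show responders by center and cohort.
3. Include baseline severity as a covariate in the optional logistic regression.
4. Name the CMH statistic, and reconcile 6.5.4, which still requires the replaced model, with 6.5.1 and 6.7. Settle in the same edit whether the follow-up regression uses categorical or numeric dose.

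The cost is a few lines of SAP text and a short program. Baseline severity is already collected, so no subjects, visits or assessments are added. In the balanced scenario with a true dose effect, the severity-stratified test gains about 10 points of power (62.7% − 52.6%). With two strata the test collapses only if each stratum is all responders or all non-responders.
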